7.3 Treatment assignment

The intention is to randomize approximately 384 subjects to the doses 5 mg, 10 mg, 20 mg, 30 mg, 40 mg of neladenoson bialanate, and placebo according to an allocation ratio of 1:2:2:2:2:3, respectively.

At the baseline visit, the investigator will first perform all required pre-treatment examinations and will then randomize the qualified patients to one of the six treatment arms.

The randomization will be stratified by atrial fibrillation (AF): yes vs. no.

Enrollment into the AF stratum may be stopped (after the discussion between the sponsor and the Steering Committee) when the AF stratum constitutes 30% of the total expected enrollment.

The randomization lists will be provided by Bayer's Global Randomization Management Group. Randomization will be done using an interactive voice / web response system (IxRS).

A handbook describing how to use the IxRS will be provided to each study site.

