10.4 Determination of sample size

In the first step, this combined proof-of-concept and Phase IIb dose-finding study has been powered for the detection of a dose response signal in the primary efficacy variable change in LVEF.

The sample size for the primary efficacy variable change in LVEF was evaluated under the assumptions described in Section 10.3.2.2 and a type I error level = 5% with the aim to achieve at least 80% power for the one-sided primary multiple contrast test. The overall randomization ratio was assumed to be 3:1:2:2:2:2 for doses 0, 5, 10, 20, 30, and 40 mg.

Table 10–2 displays the power for the multiple contrast test in the MCP-Mod approach, used as primary analysis, for the set of specified alternatives.

Table 10–2: Power for multiple contrast test for set of different alternatives

Sample size		Power for alternative based on respective dose-response model (in %)					
Overall	Per group ^a	Linear	Sigmoidal E _{max} 1	Sigmoidal E _{max} 2	E _{max}	Quadratic	Minimum
240	40	73.36	86.24	81.20	82.26	79.97	73.36
252	42	75.26	87.73	82.94	83.94	81.70	75.26
264	44	77.10	89.13	84.58	85.58	83.31	77.10
276	46	78.71	90.30	85.97	86.94	84.70	78.71
288	48	80.31	91.39	87.30	88.25	86.09	80.31
300	50	81.62	92.27	88.42	89.32	87.24	81.62
312	52	82.99	93.15	89.53	90.38	88.39	82.99
324	54	84.25	93.92	90.54	91.37	89.50	84.25
336	56	85.43	94.60	91.45	92.22	90.39	85.43
348	58	86.56	95.22	92.31	93.02	91.28	86.56

^a Number of patients randomized to dose levels 10 mg, 20 mg, 30 mg, and 40 mg of neladenoson bialanate, for placebo sample size per group to be multiplied by 3/2, for dose level 5 mg sample size per group to be divided by 2.

To achieve at least 80% power for the multiple contrast test in the MCP-Mod approach under all different alternatives, a minimum of 48 patients per treatment group (72 patients for the placebo and 24 patients for the 5 mg group) is needed, resulting in an overall sample size of N = 288 patients.

In the second step, the power for the multiple contrast test in the MCP-Mod approach for the absolute change in log-transformed NT-proBNP was estimated, based on the assumptions outlined in Section 10.3.2.2 and a given sample size of $N = 288$. Statistical simulations were used to assess the power of the Hochberg test to reject at least one of the two null hypotheses. It was concluded that an overall sample size of $N = 288$ patients is sufficient to reject at least one of the two primary efficacy hypotheses with a power of about 83%.

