5.1 Assignment of analysis sets

Final decisions regarding the assignment of subjects to analysis sets will be made during the review of study data and documented in the final list of important deviations, validity findings and assignment to analysis set(s) (see section 4.6).

Data for all patients who signed informed consent but were not randomized will not be included in any statistical analyses except standard disposition tables and listings provided in the clinical study report (Screening failures and discontinued patients).

The statistical analysis sets are defined as follows:

Full analysis set (FAS)

The FAS population consists of all randomized unique patients. According to the ICH E9 guideline, this analysis set is as complete as possible and as close as possible to the intent-to-treat (ITT) ideal. Patients will be analyzed as randomized. The FAS will be used to display baseline characteristics and to display efficacy analyses. Sensitivity analyses are based on the FAS population. For the analyses conducted in FAS, patients will be analyzed as randomized per IxRs.

Safety analysis set (SAF)

The SAF population consists of all randomized patients who received at least one dose of study medication after randomization. The SAF will be used to display safety analyses. For analyses conducted in SAF, patients will be analyzed as treated.

Per-protocol set (PPS)

The protocol defines a PPS. Since there are two primary efficacy variables, we will define PPS LVEF and PPS BNP, specific to the presence of non-missing data for each variable separately.

Per-protocol set for LVEF (PPS LVEF): The PPS LVEF population consists of all FAS population patients without validity findings. Validity findings may include adherence and compliance issues and the violation of inclusion / exclusion criteria affecting efficacy evaluation. If the left ventricular ejection fraction of this subject is measured after first dose of study medication but within a specified time frame this subject will not be excluded from PPS LVEF. The patients with invalid/missing baseline value or missing post-baseline value not due to CV death or HF hospitalization will be excluded from the PPS LVEF. The primary analysis of LVEF will be conducted in PPS LVEF.

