6.2.1.2 Primary analysis of primary efficacy variables

Primary analysis will be performed in PPS LVEF and PPS BNP respectively, a subset of the FAS comprising “compliant and adherent” patients (as much as possible, defined via validity criteria). To avoid bias, the PPS LVEF and PPS BNP will also include those “compliant and adherent” patients who are “censored” due to CV death or a hospitalization for HF preventing the assessment of the relevant efficacy endpoints 20 weeks after randomization to take place as planned. For missing post-baseline value due to CV death or study drug/study discontinuation due to HF, a worst case approach (WOV) will be applied. The worst change by treatment group will be calculated. If the worst change in that treatment group is positive for LVEF / negative for NT-proBNP, the worst case in that treatment group is 0. The missing change from baseline value will be imputed with a multiple 1.0 of the median of worst changes from baseline value among all treatment groups. The post-baseline value at week 20 will be calculated accordingly as baseline value + imputed change from baseline. If this imputed post-baseline value for LVEF is < 0% in case of CV death preventing the measurement, then the post-baseline value will be replaced with 0 and the imputed change from baseline will be modified to (- baseline value). Similarly, if the imputed post-baseline value is < 5% in case of a hospitalization for HF and no CV death preventing the measurement, the post-baseline value will be set to 5% and the corresponding imputed change from baseline will be reset to (5 - baseline value).

For both primary efficacy variables, it is planned to perform a test for a dose-response signal, respectively, under the assumption of a nearly monotone dose-response relationship in the dose range considered. The MCP-Mod method (5) combining multiple comparison procedures (MCP) principles with modeling techniques will be used for the primary statistical analysis of the primary efficacy variables. This method allows the flexibility of modeling for dose estimation, while preserving the robustness to model misspecification associated with MCP procedures. The MCP-Mod method will be used based on SAS programs provided (9) and the results may be validated within R (10) with the actual DoseFinding package (11).

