- the expected mean effect under the placebo dose is assumed as an absolute decrease from baseline of $-0.105 \log(\text{pg/mL})$ with a standard deviation of $\sigma = 0.85 \log(\text{pg/mL})$, which is equivalent to a 10% relative reduction from a mean of 2,500 pg/mL at baseline.
- while the maximum observable mean effect under neladenoson bialanate within the dose range considered is assumed as an absolute decrease from baseline of $-0.357 \log(\text{pg/mL})$ with a standard deviation of $\sigma = 0.85 \log(\text{pg/mL})$, which is equivalent to a 30% relative reduction from a mean of 2,500 pg/mL at baseline.

It is assumed that the respective primary response efficacy variable, denoted as Y , is observed for the 6 parallel groups corresponding to doses levels: (placebo =) $d_1 < d_2 < \dots < d_k$, where $k = 6$.

For patient j within treatment group i the response can then be described by the following model:

$$Y_{ij} = f(d, \theta) + \varepsilon_{ij}, \quad \varepsilon_{ij} \sim N(0, \sigma^2), \quad i = 1, \dots, k, \quad j = 1, \dots, n_i,$$

[figure not shown]
where $f(\cdot)$ is parameterized by a vector of parameters θ and ε_{ij} is the error term.

A candidate set with $M=5$ different dose response shapes $f(\cdot)$ based on four models was chosen for the MCP-Mod method. Table 6–1 displays the response expressions for the shapes in the candidate sets for both, change in LVEF and change in log-transformed NT-proBNP. Figure 6–1 shows the corresponding dose-response shapes for change in LVEF. The model parameters were obtained through discussions with experts in the clinical team, taking prior beliefs and uncertainty into account. The dose-response shapes for NT-proBNP are equivalent to those for LVEF but with decreasing trends.

Table 6–1: Dose-response shapes used in the candidate set

Model	Response as function of dose d	
	LVEF	NT-proBNP
Linear	$2 + 0.075d$	$-0.105 - 0.0063d$
Sigmoidal E_{\max} 1	$2 + 3.007689d^4 / (9^4 + d^4)$	$-0.105 - 0.2526d^4 / (9^4 + d^4)$
Sigmoidal E_{\max} 2	$2 + 3.375d^3 / (20^3 + d^3)$	$-0.105 - 0.2835d^3 / (20^3 + d^3)$
E_{\max}	$2 + 3.09375d / (1.25 + d)$	$-0.105 - 0.2599d / (1.25 + d)$
Quadratic	$2 + 0.2d - 0.00333d^2$	$-0.105 - 0.0168d + 0.00028d^2$

Figure 6–1: Dose-response shapes used in the candidate set for change in LVEF

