where $\bar{\mu} = N^{-1} \sum_{i=1}^6 \mu_{mi}^0 n_i$. In case of unequal sample sizes per treatment arm, $c_{opt,m}$ cannot be expressed in closed form and numerical optimization techniques are required (9, 11). The $c_{opt,m}$ is derived by fulfilling the condition $\sum_{i=1}^6 c_{mi}^2 = 1$.

The single contrast test for detecting the m -th model shape is defined by

$$T_m = \frac{\sum_{i=1}^6 c_{mi} \bar{Y}_i}{s \sqrt{\sum_{i=1}^6 c_{mi}^2 / n_i}}, m = 1, \dots, 5, \quad \text{where } S^2 = \frac{\sum_{i=1}^6 \sum_{j=1}^{n_i} (Y_{ij} - \bar{Y}_i)^2}{N-6}.$$

Under the null hypothesis of no dose-response effect, i.e. $\mu_{d_1} = \dots = \mu_{d_6}$, the test statistic $T = (T_1, \dots, T_5)'$ follows a central multivariate t distribution with N-6 degrees of freedom and correlation matrix $R = (\vartheta_{ij})$, where $\vartheta_{ij} = \frac{\sum_{l=1}^6 c_{il} c_{jl} / n_l}{\sqrt{\sum_{l=1}^6 c_{il}^2 / n_l \sum_{l=1}^6 c_{jl}^2 / n_l}}$.

The final test statistic T_{max} is based on the maximum contrast test and a “proof-of-concept” dose-response relationship is detected if this maximum statistic T_{max} , and thus at least one single contrast test, is statistically significant, while controlling the familywise error rate at level α . If $q_{1-\alpha}$ denotes the multiplicity adjusted critical value, a dose-response signal is established if $T_{max} \geq q_{1-\alpha}$. The smallest of the corresponding adjusted p-values will be used for the Hochberg test.

This analysis will be performed for the FAS and PPS LVEF, PPS BNP populations respectively, where the PPS LVEF and PPS BNP analysis is the primary analysis.

If no candidate model is statistically significant, the procedure stops, indicating that a dose-response relationship cannot be established from the observed data.

Out of the statistically significant models in the candidate set a best model can be selected for the next step: modeling and estimation.

Step 2: Modeling and estimation of target doses

If a dose-response signal is established, the selected dose-response model(s) will be fitted to the observed data to estimate the model parameters.

The estimated dose-response model will be plotted against the doses including 90% confidence bands. Once the dose-response model has been successfully fitted to the data, target dose(s) of interest are estimated. Given a clinically relevant effect Δf , a minimum effective dose (MED_{Δ}) associated with model $f(d, \theta)$ is defined as

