6.2.1.4.2 Sensitivity analysis of primary efficacy variables in FAS

Additional efficacy analyses in the FAS will include the following:

- Primary analyses of primary efficacy variables specified in section 6.2.1.2 will be performed in FAS without any imputation.
- Generally, it will be assumed that missing observations for the respective efficacy variables are missing at random. This implies that the behavior of the post dropout observations can be predicted from the observed variables using appropriate imputation models. Likely exceptions to the missing at random assumption are observations which are missing due to a patient’s CV death or HF hospitalization prior to the visit in Week 20. These observations can be assumed to be missing not at random (MNAR), i.e., that missingness depends both on observed and unobserved outcomes and that an explicit model for the patient’s statistical behavior after drop-out (or death) is required. Therefore, an analysis based on a pattern mixture framework (6) with different imputation rules depending on the reason for missingness will be used using a multiple imputation model, followed by a modification of the imputed data applying penalties:
 1. First, multiple imputation will be applied to draw sets of completed data, using an appropriate imputation model. Baseline characteristics which should be considered in the imputation model include but are not restricted to the baseline values of the respective efficacy variable, the treatment group, and sex.
 2. The imputed data will be modified by applying penalties. The penalty is chosen as the median of the worst changes from baseline across treatment groups (or 0 if the median worst change should be positive for LVEF or negative for LVESV/LVEDV or log-transformed NT-proBNP/hs-TNT).

3. After modifying the completed data sets, the primary analysis specified in section 6.2.1.2 will be applied to the multiple imputed datasets and the point estimate and variance of the contrast from multiple imputed datasets will be combined based on Rubin's rule (8). For more details see Appendix 9.4.
- Primary analyses where for each patient without an observation at the visit in Week 20 the missing value will be imputed according to a last observation carried forward approach, including the baseline value.

For reproducibility, the SAS seed number for creating the random numbers for the multiple imputation will be set to the study number.

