6.2.1.5 Additional analysis of primary efficacy variables

Adjusted primary analysis of primary efficacy variables specified in section 6.2.1.2 (dose-response test) will be performed in PPS LVEF and PPS BNP respectively. Baseline values of atrial fibrillation, eGFR (≤ 60 mL/min/1.73m², >60 mL/min/1.73m²), gender, age group (<50 , 50-75 and >75), and BMI > 30 kg/m² will be used as covariates. In exploratory manner, the absolute change in LVEF (%) from baseline to week 20 will be categorized into four groups (≤ -5 , > -5 to <5 , 5 to <10 , ≥ 10). The number (%) of patients in each category of LVEF will be displayed by treatment group and overall. For further details including further categorization see the TLF Specification document.

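### The primary dose-response test adjusts for neither the endpoint's baseline value nor the AF randomisation stratum, and the planned adjusted test also omits the baseline value

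*SAP*

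**What the plan says.** SAP 6.2.1.2 (Assumptions) states that "the response can then be described by the following model" and then writes the outcome as a dose function plus normal error with a common variance. In Step 1 each contrast statistic is built from raw arm means and a pooled within-arm variance, and the vector of five statistics "follows a central multivariate t distribution with N-6 degrees of freedom". Six fitted means account for all the degrees of freedom used, so nothing else is in the model. Protocol 10.3.2.2 gives the same model.

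Protocol 7.3 says: "The randomization will be stratified by atrial fibrillation (AF): yes vs. no". AF is not in the primary test.

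SAP 6.2.1.5 repeats the dose-response test with covariates. The list begins "Baseline values of atrial fibrillation, eGFR" and continues with gender, age group and BMI. Baseline LVEF and baseline log NT-proBNP are not on it.

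Elsewhere the SAP treats those baseline values as informative. The variables for the FAS imputation model in 6.2.1.4.2 "include but are not restricted to the baseline values of the respective efficacy variable", and baseline LVEF and NT-proBNP both define key subgroups in 4.5.4.

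**The concern.** A change score removes the baseline value with a fixed slope of 1. Unless the true slope of Week 20 on baseline is 1, change still correlates with baseline, and variance that could be explained stays in the error term. The dose-response test and the target-dose estimate are then less precise than the same data allow.

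Chance imbalance is also only partly handled. With equal variances at the two visits and baseline to Week 20 correlation r, a fraction 1 − r of a baseline difference between arms passes into the difference in mean change, with reversed sign. The 5 mg arm is planned at only 24 evaluable patients, so such imbalance is a practical possibility.

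The planned adjusted test does not close the gap. It does not feed the Hochberg decision, and it leaves out the endpoint's own baseline. AF would help only if it predicts the change, and the documents give no figure for that.

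**Working it through.** **Inputs from the documents.** Evaluable sample 288, split 72/24/48/48/48/48 over 0, 5, 10, 20, 30 and 40 mg (protocol 10.4). LVEF: linear slope 0.075 per mg, SD 7. Log NT-proBNP: linear slope 0.0063 per mg in absolute value, SD 0.85 (protocol 10.3.2.2). One-sided 5%.

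**Assumed, because the documents do not give it.** ρ, the absolute correlation of change with baseline, is taken over 0 to 0.5. AF is assumed to explain nothing.

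**Step 1: reproduce the plan's figures.** Contrasts proportional to n_i(μ_i − μ̄), scaled to unit length, match SAP Table 6-2 to within 0.001. The critical value of the maximum of five correlated t statistics on 282 df is about 1.96. Simulated LVEF power under the linear shape is 80.2%, against 80.31% in protocol Table 10-2. The other four shapes give 91.3, 87.2, 88.3 and 86.1%, against 91.39, 87.30, 88.25 and 86.09%.

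For a hand check of the linear contrast:
- Mean dose = 4920/288 = 17.08.
- Σn_i(d_i − d̄)² = 144,600 − 288 × 17.083² ≈ 60,550, with square root 246.1.
- Noncentrality = 246.1 × 0.075/7 = 2.64 for LVEF and 246.1 × 0.0063/0.85 = 1.82 for NT-proBNP.

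**Step 2: adjust.** With two covariates fitted, the effective SD is σ√(1 − ρ²) × √(1 + 2/(N − 9)). The last factor, √(1 + 2/279) = 1.0036, is the cost of the covariates. At ρ = 0.5 the LVEF noncentrality becomes 2.64/(0.866 × 1.0036) = 3.03.

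| | LVEF power, linear | NT-proBNP power, linear |
|---|---|---|
| Unadjusted | 80.2% | 52.6% |
| Adjusted, ρ = 0 | 80.0% | 52.4% |
| ρ = 0.2 | 81.4% | 53.8% |
| ρ = 0.3 | 83.2% | 55.7% |
| ρ = 0.4 | 85.8% | 58.7% |
| ρ = 0.5 | 89.1% | 62.9% |

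**Step 3: what ρ means in terms of r.** With equal variances ρ = √((1 − r)/2), so r = 0.5, 0.7, 0.8 and 0.9 give ρ = 0.50, 0.39, 0.32 and 0.22. If the baseline SD is 0.8 of the Week 20 SD, r = 0.5, 0.7 and 0.8 give ρ = 0.33, 0.14 and 0.00.

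**Step 4: effect of worst-case imputation.** Missing changes after CV death or an HF event are "imputed with a multiple 1.0 of the median of worst changes from baseline value among all treatment groups", which weakens the link with baseline. LVEF was simulated at patient level with 12,000 trials per cell, baseline as the only covariate, an assumed baseline mean of 28 and SD of 7, and equal imputation rates in all arms. For simplicity the 5% floor was applied to every imputed value, although the SAP uses 0 for CV deaths. Power, unadjusted then ANCOVA:

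| Share imputed | ρ = 0 | ρ = 0.3 | ρ = 0.5 |
|---|---|---|---|
| None | 80.6 / 80.5 | 80.3 / 83.6 | 80.7 / 89.3 |
| 5% | 70.6 / 70.5 | 70.7 / 73.0 | 70.7 / 78.4 |
| 10% | 62.8 / 62.9 | 62.3 / 64.7 | 62.8 / 68.6 |

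At ρ = 0.5 the gain falls from 8.6 to 7.7 to 5.8 points. Type I error at ρ = 0.5 (unadjusted, ANCOVA) was 5.0% and 5.0% with none imputed, and 4.7% and 5.0% with 5% imputed. The Monte Carlo standard error is about 0.4 point on power and 0.2 on type I error.

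**Step 5: the Hochberg success rule.** For the linear shape with uncorrelated endpoints, unadjusted power to reject at least one hypothesis is 83.5%, consistent with the plan's figure of about 83%. With an assumed endpoint correlation of 0.3 it is 79.5%. Baseline adjustment under equal variances raises that to 81.7% (r = 0.9), 83.5% (0.8), 85.6% (0.7) and 89.3% (0.5), before the small cost of fitting covariates.

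**The case against.** The strongest reply is that nothing is wrong. The unadjusted test is unbiased under randomisation, and model, contrasts and power table agree with one another. The sample size meets its stated aim ("To achieve at least 80% power for the multiple contrast test in the MCP-Mod approach under all different alternatives"). An adjusted test including the stratification factor is already planned, and the primary analyses are repeated in subgroups defined by baseline LVEF and NT-proBNP. All of that stands, so this is a point about efficiency only.

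The gain may also be small. The largest figures need ρ = 0.5, which under equal variances means a baseline to Week 20 correlation of only 0.5. At r = 0.8 to 0.9 the LVEF gain is roughly 1.5 to 3.5 points. If baseline is less variable than Week 20, it can vanish. Eligibility limits on LVEF and natriuretic peptides may narrow the baseline spread. The linear shape is the least powerful one for LVEF; at ρ = 0.5 the other four gain about 5 to 7 points. These limits stand, and the upper end of the range should not be read as the expected gain.

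Three practical points also stand. The protocol carries the same model and must change with the SAP. The AF variable needs a definition. SAP 5.1 keeps patients whose endpoint was measured shortly after the first dose; if that includes baseline values, the covariate is post-dose for them, as the change score already is.

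None of this removes the point. The adjusted test does not decide success and omits the endpoint's baseline, and subgroup analyses do not recover the lost precision.

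**Conclusion.** The concern holds as an efficiency point. The primary test uses no covariates, and the adjusted test leaves out the variable most directly tied to the endpoint. Over the assumed range ρ = 0 to 0.5, the power change at N = 288 under the linear shape runs from a loss of 0.2 point to a gain of 8.9 points for LVEF (89.1 − 80.2) and 10.3 points for NT-proBNP (62.9 − 52.6). These figures assume that AF explains nothing and that no values are imputed; imputation lowers the gain.

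Confidence that the covariates are omitted is high. Confidence in the size of the gain is low, because the documents give neither the baseline to Week 20 correlation nor the baseline SD. The case for changing rests on the asymmetry: a near-zero cost if baseline explains nothing, and a useful gain if it explains a moderate share. For LVEF the linear shape is also where the plan's margin over 80% is thinnest, at 0.31 point.

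**What to change.** - **Primary analysis (SAP 6.2.1.2).** Estimate the six dose means by ANCOVA with the endpoint's baseline (LVEF, or log NT-proBNP) and AF (yes/no) as covariates. Use the adjusted means and their covariance matrix in the multiple contrast test and in the modelling step.
- **Formulas.** Rewrite the contrast, correlation and degrees-of-freedom text to match. Six means plus two covariates leave N − 8, or 280 at N = 288.
- **AF.** State whether it is the stratum recorded at randomisation or clinical AF.
- **Sensitivity.** Keep the unadjusted test as a sensitivity analysis.
- **SAP 6.2.1.5.** Add the endpoint's baseline to the covariates. If nothing else is changed, this one-line edit is still worthwhile.
- **Missing or late baseline.** State that patients without a baseline value are handled as now. SAP 5.1 already says: "The patients with invalid/missing baseline value or missing post-baseline value not due to CV death or HF hospitalization will be excluded". In the FAS their change score is undefined without imputation. Say also how a baseline value taken after the first dose is treated.
- **Protocol 10.3.2.2.** Make the same change there, so that the two documents agree.

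Fix this before unblinding. The cost is wording in both documents and modest programming, since a covariate-adjusted dose-response test is already planned. No new data or visits are needed, and no patients are lost from the primary analysis sets. The power cost is about 0.2 point if the covariates explain nothing.
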